### **9.4.6. Electrocardiograms**

For each patient, ECGs should be collected according to the Schedule of Activities (Section 2).

Any clinically significant findings from ECGs that result in a diagnosis and that occur after the patient receives the first dose of the investigational product should be reported to Lilly, or its designee, as an AE via eCRF.

For each patient, a single 12-lead digital ECG will be collected according to the Schedule of Activities. ECGs must be recorded and reviewed before receiving study treatment. Subjects must be supine for at least 10 minutes before ECG collection and remain supine but awake during ECG collection. ECGs may be obtained at additional times, when deemed clinically necessary. All ECGs recorded should be stored at the investigational site.

ECGs will be interpreted by a qualified physician (the investigator or a qualified designee) at the site as soon after the time of ECG collection as possible, and ideally while the patient is still present, to determine whether the patient meets entry criteria at the relevant visit(s) and for immediate patient management, should any clinically relevant findings be identified.

If a clinically significant finding is identified (including, but not limited to, changes in QT/QTc interval from baseline) after enrollment, the investigator will determine if the patient can continue in the study. The investigator, or a qualified designee, is responsible for determining if any change in patient management is needed, and must document his/her review of the ECG printed at the time of collection. Any new clinically relevant finding should be reported as an AE.

### **9.4.7. Safety Monitoring**

The Lilly clinical pharmacologist or CRP/scientist will monitor safety data throughout the course of the study.

Lilly will review SAEs within time frames mandated by company procedures. The Lilly clinical pharmacologist or research physician will consult with the functionally independent Global

Patient Safety therapeutic area physician or clinical research scientist when appropriate, and periodically review:

- trends in safety data
- laboratory analytes
- AEs

In the event that safety monitoring uncovers an issue that needs to be addressed by unblinding at the group level, additional analyses of the safety data will be conducted by the personnel included in the Unblinding/Blinding Plan.

#### 9.4.7.1. Glucose Monitoring

Hypoglycaemia will be described using the following definitions:

- **Documented hypoglycaemia:**
  - **Symptomatic hypoglycaemia:** an event during which typical symptoms of hypoglycaemia are accompanied by plasma glucose  $\leq 70$  mg/dL (3.9 mM)
  - **Asymptomatic hypoglycaemia:** an event not accompanied by typical symptoms of hypoglycaemia but with plasma glucose  $\leq 70$  mg/dL (3.9 mM)
- **Unspecified hypoglycaemia:** an event during which plasma glucose is  $\leq 70$  mg/dL (3.9 mM) but no information relative to symptoms of hypoglycaemia was recorded
- **Probable symptomatic hypoglycaemia:** an event during which symptoms indicative of hypoglycaemia are not accompanied by a plasma glucose determination (but that was presumably caused by plasma glucose  $\leq 70$  mg/dL [3.9 mM])
- **Severe hypoglycaemia:** an event requiring assistance of another person to actively administer carbohydrate, glucagon, or other resuscitative actions. During these episodes, the subject has an altered mental status, and cannot assist in their care, is semiconscious or unconscious, or experiences coma with or without seizures, and may require parenteral therapy. Plasma glucose measurements may not be available during such an event, but neurological recovery attributable to the restoration of blood glucose concentration to normal level is considered sufficient evidence that the event is induced by a low plasma glucose concentration ( $\leq 70$  mg/dL [3.9 mM])
- **Nocturnal hypoglycaemia:** any hypoglycaemic event (documented symptomatic, asymptomatic, probable symptomatic, or severe hypoglycaemia) that occurs between bedtime and waking
- **Relative hypoglycaemia:** an event during which typical symptoms of hypoglycaemia, that do not require the assistance of another person, are accompanied by plasma glucose  $> 70$  mg/dL (3.9 mM), but these levels may be quickly approaching the 70 mg/dL (3.9 mM) threshold
- **Overall (or total) hypoglycaemia:** This optional category combines all cases of hypoglycaemia. If an event of hypoglycaemia falls into multiple subcategories, the event is only counted once in this category

The goal of the euglycaemic clamp is to maintain blood glucose concentrations at normoglycaemic levels close to a pre-defined target. Therefore, plasma glucose concentrations

below 70 mg/dL (equivalent to blood glucose 63 mg/dL) will not routinely be recorded as hypoglycaemic events during the glucose clamp procedure. However, at the discretion of the investigator, decrease in glucose concentrations may be recorded as a hypoglycaemic event based on clinical concern, or related to technical issues resulting in hypoglycaemia.

#### **9.4.7.1.1. Severe Hypoglycaemia**

The determination of a hypoglycaemic event as an episode of severe hypoglycaemia, as defined above, is made by the investigator based upon the medical need of the subject to have required assistance and is not predicated on the report of a subject simply having received assistance.

Only severe hypoglycaemic episodes will be reported as AEs. All episodes of severe hypoglycaemia will be reported as SAEs.

#### **9.4.8. Injection-Site Assessments (Local Tolerability)**

Injection-site assessments for local tolerability will be conducted as specified in the Schedule of Activities and more frequently if deemed necessary by the investigator (Section 2).

Local tolerability at the injection site will be evaluated by means of assessments within the following categories: pain (including burning), itching, erythema, edema, and induration/infiltration.

Additional assessments will be performed until resolution, as judged necessary by the investigator.

Digital pictures may be taken of the injection site at the time of identification of local intolerability and thereafter as judged as necessary by the investigator. The pictures should include subject number, visit number, time after injection, and a ruler for scaling.

An injection-site reaction should be recorded as either an AE or an SAE according to respective definitions/criteria.

##### **9.4.8.1. Pain Measurements Using the Visual Analog Scale**

Pain measurements will be assessed using the electronic version of the 100-mm validated visual analog scale (VAS) (or electronic VAS [eVAS]) for pain. The VAS is a well validated tool (Williamson and Hoggart 2005) to assess injection-site pain.

The eVAS (van Duinen et al. 2008) is presented as a 10-cm (100-mm) line, anchored by verbal descriptors, usually “no pain” and “worst imaginable pain.” The patient will be asked to mark the 100-mm line electronically to indicate pain intensity associated with each injection on a scale of 0 (no pain) to 100 mm (worst imaginable pain) according to the Study Schedule and as clinically indicated.

As injection-site pain is an expected AE injection-site pain (especially transient episodes of pain) will generally not be considered a clinically significant event unless the duration or intensity of the pain interferes with normal activities of daily living or constitutes a risk to the wellbeing of the subject. Analgesia can be prescribed in response to pain and must be documented in the concomitant medication section of the CRF.

#### 9.4.9. Immunogenicity Assessments

Blood samples for immunogenicity testing will be collected to determine antibody production against insulin lispro as described in the Schedule of Activities (Section 2). Additional samples may be collected if there is a possibility that an AE is immunologically mediated.

Immunogenicity will be assessed by a validated assay designed to detect antidrug antibodies in the presence of insulin lispro.

Serum from the blood sample will be divided into 3 aliquots; the first aliquot is used for initial testing and the remaining aliquots will be stored at  $-70^{\circ}\text{C}$ , and retained for a maximum of 15 years after the last subject visit, or for a shorter period if local regulations and ERBs allow, at a facility selected by the sponsor. The duration allows the sponsor to respond to future regulatory requests related to the study insulins. Any samples remaining after 15 years will be destroyed.

### 9.5. Pharmacokinetics

At the visits and times specified in the Schedule of Activities, venous blood samples of approximately 2.5 mL each will be collected to determine serum concentrations of insulin lispro, and samples of approximately 2.0 mL each will be collected to determine plasma concentrations of treprostinil. Instructions for the collection and handling of blood samples will be provided by the sponsor. The actual date and time (24-hour clock time) of each sampling will be recorded.

#### 9.5.1. Bioanalysis

Serum concentrations of insulin lispro will be measured using a CCI [REDACTED] specific for insulin lispro at a laboratory approved by the sponsor. Plasma concentrations of treprostinil will be measured using a validated CCI [REDACTED] at a laboratory approved by the sponsor. Samples will be retained for a maximum of 1 year after the last subject visit. During this time, plasma and serum remaining may be used for other exploratory analyses on insulin lispro or treprostinil.

### 9.6. Glucodynamics (Euglycaemic Glucose Clamp)

The aim of the euglycaemic glucose clamp is to maintain target glucose levels through infusion of a 20% D-glucose (dextrose) solution after the administration of a dose of insulin. During the glucose clamp, the GIR will be adjusted to maintain a predetermined target blood glucose concentration for the individual subject. Thus, blood glucose concentrations are kept constant while the GIR varies. The varying GIR will then reflect the GD activity of insulin.

Subjects with T1DM will participate in euglycaemic glucose clamps on 2 separate visits. All glucose clamp procedures will be performed after an overnight fast of at least 8 hours.

Approximately 1-6 hours before the planned administration of study drug, subjects will be connected to the clamp device for continuous blood glucose monitoring and receive a variable IV infusion of either insulin glulisine or glucose to obtain a steady blood glucose clamp target of 100mg/dL ( $\pm 20\%$ ) (5.5 [ $\pm 1.1$ ] mmol/L). The target blood glucose level of 5.5 mmol/L (100 mg/dL)  $\pm 20\%$  (upper and lower limits included) must be kept at -60 to -30 minutes before trial product administration, followed by a target blood glucose level of 5.5 mmol/L (100

mg/dL)±10% (upper and lower limits included) the last 30 minutes prior to trial product administration without any glucose infusion. The intravenous insulin infusion (if any) is lowered as much as possible to keep the BG concentrations at the target without having to infuse glucose. The insulin infusion is tapered off and should be stopped 10 minutes prior to dosing. Baseline is defined as the mean of blood glucose concentrations at -6, -4, and -2 minutes before trial product administration as measured using CCI [REDACTED], and the onset of action occurs when blood glucose drops to 0.3 mmol/L (5 mg/dL) from baseline. If there are no stable BG measurements using CCI [REDACTED] in the last minutes before intended dosing, dosing should be postponed and the run-in period will be prolonged. If the target blood glucose level cannot be established before 1400 hours, the visit will be terminated and the subject may be rescheduled for a new dosing visit 1 to 7 days later. After the onset of action has been reached, a variable IV glucose infusion will be initiated in order to keep BG constant at the target level (5.5 mmol/L; 100 mg/dL). The GIR necessary to keep the BG concentration at the target level will be recorded every minute throughout the glucose clamp. Frequently or at least every 30 minutes throughout the glucose clamp, BG measurements for safety will be performed using CCI [REDACTED].

The clamp procedure will continue for up to 10 hours after dose or until after blood glucose concentrations increased to >200 mg/dL (11.1 mmol/L) without any glucose being administered for at least 30 minutes, whichever is earlier.

At the end of the clamp procedure, the patient will receive a medical assessment, and be given a meal along with their prandial insulin treatment. Their basal insulin regimen may be restarted accordingly, albeit subjected to the stopping guidance as described in Section 5.1, prior to the next dosing visit, if applicable.

The sample(s) will be stored for up to a maximum of 1 year after the last patient visit for the study at a facility selected by the sponsor.

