### 10.3. Statistical Analyses

Statistical analysis of this study will be the responsibility of Lilly.

The primary statistical analyses for PK will be conducted on those subjects who receive at least 1 dose of study drug and have measurable insulin lispro concentrations. The primary statistical analysis for GD will be conducted on those subjects who complete at least 1 clamp procedure. Supportive analyses will be done on the key parameters for the subjects who complete all treatment periods with evaluable data. Safety analyses will be conducted for all enrolled subjects who receive at least 1 dose of study drug, whether or not they complete all protocol requirements.

Any change in the data analysis methods described in the protocol will require an amendment only if it changes a principal feature of the protocol. Any other change to the data analysis

methods described in the protocol and the justification for making the change will be described in the study results.

Summary statistics (including number of subjects, mean, standard deviation or standard error, minimum, and maximum) will be presented for continuous variables. A linear mixed-effect model will be used for continuous variables unless otherwise stated in the below subsections. The primary comparison between LY900014 and insulin lispro for each age group will be performed using the model that includes treatment, sequence, and period as fixed effects, and subject within sequence as a random effect. Unless otherwise noted, all tests of treatment effects will be conducted at a 2-sided alpha level of 0.05, and CIs will be calculated at 95%, 2-sided.

An exploratory analysis on the interaction between treatment and age group will be assessed using data from both age groups by a model similar to that for each age group, with the addition of age group and the interaction of treatment by age group as fixed effects. This test will be used to compare whether the LY900014 versus insulin lispro treatment effect is similar between the elderly and younger adult groups.

Additional exploratory analyses of the data will be conducted as deemed appropriate. Study results may be pooled with the results of other studies for population PK analysis purposes to avoid issues with post-hoc analyses and incomplete disclosures of analyses.

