9.4.2 Glucodynamic Statistical Inference

The GD parameters will be listed and summarized by treatment and age group.

The statistical model will be the same as the model used for the analysis of the PK parameters. The non-time variables will be log-transformed prior to analysis and will include R_{max} , G_{tot} , $G_{\text{tot}}(0-30\text{min})$, $G_{\text{tot}}(0-1\text{h})$, and $G_{\text{tot}}(0-10\text{h})$. For GD parameters that have at least 1 patient with a value equal to zero, a value equal to the smallest non-zero observed GD value for that parameter divided by 2 will be added to all values, and the analysis of the log-transformed data will be performed.

The same model without log-transformation will be used for the analysis of the GD time parameters (T_{onset} , TR_{max} , early 50% TR_{max} , and late 50% TR_{max}). Least-squares means, treatment differences in least-squares means, and the corresponding 95% CIs for the treatment differences will be estimated from the model. The treatment ratios and 95% CIs for the ratios will be calculated using Fieller's Theorem

All analyses will be repeated for the population of patients who complete the study.

An exploratory analysis on the interaction between treatment and age group will be assessed using data from both age groups by a model similar to that for each age group, with the addition of age group and the interaction of treatment by age group as fixed effects. This test will be used to compare whether the LY90014 versus insulin lispro treatment effect is similar between the elderly and younger adult groups. The analysis will include all GD parameters analysed previously (both untransformed and log-transformed GD parameters).

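### Early glucose infusion depends on each day's pre-dose glucose, which the trial records in every period but the glucodynamic model leaves out

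*Protocol*

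**What the plan says.** Protocol 9.6 sets four rules that matter here.

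- **Pre-dose window.** Over the final half hour before dosing, glucose must lie within 100 "mg/dL)±10% (upper and lower limits included) the last 30 minutes prior to trial product administration without any glucose infusion". That is 4.95 to 6.05 mmol/L.
- **Baseline.** "Baseline is defined as the mean of blood glucose concentrations at -6, -4, and -2 minutes before trial product administration". One value is obtained in each period.
- **Trigger.** "the onset of action occurs when blood glucose drops to 0.3 mmol/L (5 mg/dL) from baseline", which I read as a fall of 0.3 mmol/L below that baseline.
- **Target.** After onset, "a variable IV glucose infusion will be initiated in order to keep BG constant at the target level (5.5 mmol/L; 100 mg/dL").

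Earlier in the same section the target is described differently: "the GIR will be adjusted to maintain a predetermined target blood glucose concentration for the individual subject". The only value given for it is 5.5 mmol/L.

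For the analysis, SAP 9.4.2 states: "The statistical model will be the same as the model used for the analysis of the PK parameters". Protocol 10.3 describes that model as "the model that includes treatment, sequence, and period as fixed effects, and subject within sequence as a random effect", and the example code in SAP 9.3.2 carries no covariate. Baseline glucose is used only to define onset. The sole planned repeat of the glucodynamic analyses is in completers.

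**The concern.** The trigger is relative to the subject's own starting glucose, but the target is absolute. Two clamps on the same subject with the same formulation can therefore call for different amounts of early glucose, only because they started at different points in the permitted band. A low start needs extra glucose to climb to 5.5 mmol/L. A high start needs none until glucose has fallen further.

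This enters Gtot(0-30min) and Gtot(0-1h) directly. It can also shift early 50% TRmax, by changing the early shape of the infusion curve. The crossover removes only the part of pre-dose glucose that is constant within a subject, and the run-in sets the starting value afresh in each period.

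At stake is precision on endpoints that both documents list among the main glucodynamic parameters. Their stated power is about 85% for the two Gtot endpoints and 80% for early 50% TRmax, against 95% for the primary PK endpoints.

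**Working it through.** **1. What the clamp rule implies** (inputs from Protocol 9.6)

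Gap to target at onset = 5.5 − (baseline − 0.3).

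- Baseline 4.95: onset at 4.65, which is 0.85 mmol/L below target.
- Baseline 5.50: onset at 5.20, which is 0.30 below target.
- Baseline 6.05: onset at 5.75, which is 0.25 above target, so the target does not yet call for glucose.

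The spread is 0.85 + 0.25 = 1.10 mmol/L. This is the extreme case, with the two clamps at opposite limits. To express it as glucose, assume a distribution volume of 0.15 to 0.25 L/kg and a body weight of 56 to 85 kg (neither range is a plan figure, although Protocol 5.5 puts the lowest weight near 56 kg):

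- 1.10 × 0.18016 g/mmol × 0.15 × 56 = 1.7 g
- 1.10 × 0.18016 g/mmol × 0.25 × 85 = 4.2 g

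The documents give no typical early Gtot to set this against.

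**2. Chance imbalance**

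Assume baselines are uniform over the band and independent between periods.

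- SD of one baseline = 1.1/√12 = 0.318 mmol/L.
- SD of the within-subject difference = 0.318 × √2 = 0.449.
- Standard error at n = 34 = 0.449/√34 = 0.077.
- 95% range of the treatment mean difference = ±1.96 × 0.077 = ±0.15 mmol/L.

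With a tighter baseline SD of 0.15, the range is ±0.07.

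**3. The plan's own power figures** (Protocol 10.1, SAP 7)

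Method: noncentral t on the within-subject log difference, n = 34, two-sided alpha 0.05, df = 32.

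- AUC(0-30min): effect ln 1.4 = 0.336, stated SD 0.5. Power is 96.7%, against about 95% stated, so the method comes close to the plan's figure.
- Gtot: no SD is given, so the 85% cannot be reproduced. Solving for the SD that gives 85% power at ln 1.4 yields 0.635.

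**4. Effect of adjusting Gtot**

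Let r be the correlation between the within-subject difference in baseline and the within-subject difference in log Gtot. The adjusted SD is 0.635 × √(1 − r²), with df = 31. The documents do not give r, so I show a range that includes values at which adjustment hardly helps.

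| Assumed r | Adjusted SD | Power | CI width reduced by |
|---|---|---|---|
| 0 | 0.635 | 84.9% | 0% |
| 0.1 | 0.632 | 85.3% | 0.5% |
| 0.2 | 0.622 | 86.3% | 2% |
| 0.3 | 0.606 | 88.1% | 5% |
| 0.4 | 0.582 | 90.4% | 8% |
| 0.5 | 0.550 | 93.3% | 13% |

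The width column is 1 − √(1 − r²). Losing one degree of freedom changes it by only about 0.1 point.

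I give no such table for early 50% TRmax. SAP 9.4.2 analyses it untransformed, and no SD on that scale is available.

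**The case against.** The strongest reply is that nothing in the planned analysis is invalid. Treatment order is randomised, and the subject and investigator are blinded, so pre-dose glucose has no reason to differ systematically by formulation. That stands. A reader might infer that the treatment comparison is biased; the documents do not support this.

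Second, the gain is assumed. No glucodynamic SD, typical early Gtot or correlation is given, and at r of 0.2 or less the gain in Gtot power is under 1.5 points. That also stands, and it limits how strongly the change can be pressed.

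Third, 1.1 mmol/L is a worst case. Protocol 9.6 also has the insulin infusion adjusted to hold the target, and postpones dosing when the last readings are unstable. Actual differences between periods are likely to be smaller. This reduces the effect but does not remove it.

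Fourth, a reader might extend the point to T_onset. That does not follow. T_onset is defined as a fall from the subject's own baseline and does not involve the 5.5 mmol/L target. Nor can the 80% power for the time endpoints be turned into a gain through a log-scale SD, since they are not analysed on that scale.

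Fifth, Appendix 5 of the protocol says the analyses were aligned with other studies in the programme. This is a fair reason to keep the unadjusted result in the report, but not a reason to omit an adjusted one.

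**Conclusion.** The point holds as a cheap improvement in precision. By the protocol's own clamp rule, Gtot(0-30min) and Gtot(0-1h) carry a component from that day's pre-dose glucose. Early 50% TRmax may do so less directly. The planned model has no term for it, and the crossover does not remove it.

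The consequence is added within-subject noise and chance imbalance: about ±0.15 mmol/L in the treatment mean difference (95%) if baselines are uniform in the band, and less if they are tighter. The possible gain in Gtot power runs from nothing to about 8 points for correlations up to 0.5. This rests on a back-solved SD of 0.635 and on correlations that the documents do not supply.

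Separately, the wording in Protocol 9.6 about a target for the individual subject does not sit clearly with the single 5.5 mmol/L target later in that section. The dependence described here assumes that 5.5 mmol/L applies to everyone.

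**What to change.** In SAP 9.4.2, for Gtot(0-30min), Gtot(0-1h) and early 50% TRmax:

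- Pre-specify the period's baseline glucose (mean of the −6, −4 and −2 minute values) as a covariate.
- Enter it as two terms, the subject's mean over the two periods and the deviation from that mean. The within-subject effect is then not mixed with the between-subject one.
- For subjects with one completed clamp, who belong to the primary glucodynamic population under SAP 8, use the single value as the mean and set the deviation to zero.
- Report the currently planned unadjusted model alongside, for comparability across the programme.

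Leave T_onset as planned. Reconcile the two descriptions of the clamp target in Protocol 9.6.

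The cost is SAP wording and one or two degrees of freedom, about 0.1 point of Gtot power if baseline explains nothing. No new data or change to the clamp is needed. The adjustment also assumes a linear effect of baseline on log Gtot. Since the mechanism adds or removes an amount of glucose, that is an approximation, and it may be poorest where early totals are near zero. Fixing the covariate before unblinding matters, because the same adjustment chosen afterwards could look selected.
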